active k. History or signs or symptoms of gallbladder/biliary disease (e.g. previous episodes of cholestasis/biliary tract obstruction, cholelithiasis, cholecystitis, etc.). Of note, history of cholecystectomy and no active biliary signs or symptoms, is not an exclusion criterion. 8. Current physical/rehabilitation therapy (except for passive physical therapy. However, this should not be initiated the week before an evaluation visit and once started, it should be maintained over the study duration). Phase: Phase 2 – with therapeutic intervention **Description of** Sites/Facilities 23 clinical investigation sites in the US and in Europe **Enrolling Participants: Description of Study** Oral treatment with BIO101 dosing of 350 mg b.i.d. or 175 mg b.i.d. or Intervention: placebo (identical capsules). The BIO101 active principle ingredient is 20 hydroxyecdysone (20E),

> he study drug is packaged in individual blisters containing capsules and contained in an elderly- friendly weekly paper box for a monthly kit.

COVID-19 pandemic Due to the coronavirus disease 2019 (COVID-19) outbreak, the implementation of clinical protocol is affected, including but not limited to the scheduled site visit for safety and/or efficacy, site visit for monitoring, investigational product delivery, collection of adverse events and concomitant medication. Following GCP guidance to the situation of the public health emergencies, the core consensus guidelines for clinical trial management and the study DSMB recommendation, below measures have been taken:

- No additional activity of prescreening, screening and randomization will be performed during the COVID-19 outbreak. Because of the potential impact of the COVID-19 outbreak leading to the withdrawals and lost-tofollow ups from the study, these activities may resume after the COVID-19 outbreak.

- the complete assessment and tests per protocol requiring on-site visits have been suspended. every investigational visit within the protocol will now be performed remotely (e.g. by phone) for all participants still active in the study by the investigational site staff. These calls will be used to continue monitoring the health status of the participants by collecting information on Concomitant Medication (CM) and Adverse Events (AE). In addition, study questionnaires will be administered and study drug intake will also continue to be monitored following the same schedule.

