1.3 SCHEDULE OF ACTIVITIES (SOA)

During the COVID-19 outbreak, no additional activity of prescreening, screening and randomization will be performed based on GCP guidance on the situation of the public health emergencies, the core consensus guidelines for clinical trial management and the DSMB recommendation, during the COVID-19 outbreak. For all active participants in the study, measures are as follows:

- Screening activities listed below are being put on hold:
 - Activities can be performed only after the participant has signed the ICFs
 - SPPB should be performed prior to DEXA and ultrasound scans
 - DEXA can be conducted only after the medical history, concomitant medications, physical exam, and SPPB inclusion criteria are met
 - DEXA results can be collected for the study if a DEXA scan was conducted for a non-study related purpose within 8 weeks prior to the randomization date
 - Gallbladder ultrasound can be conducted, only if the medical history, concomitant medications, physical exam, SPPB and DEXA exclusion criteria are met
 - The 400MW test must be the last activity performed during the screening period and within 48 hours of randomization. This last screening assessment can be performed on the same day as the baseline visit, but it must be performed **before randomization and baseline assessments** occur
- Randomization is being put on hold:
 - Randomization can occur only after all screening assessments results are available, specifically blood tests results for safety reasons
- Baseline (Day 0) is being put on hold:
 - All baseline assessments are performed only after randomization
 - Extra blood sampling will be performed for participants partaking in the Population PK (Pop-PK) sub-study at Day 1
- M1 Visit is replaced by a telephone call
 - Safety focused phone call after the first month of investigational treatment
- M3 visit is replaced by a telephone call
 - Intermediate phone call for safety and fora reduced number of efficacy measurements (ePRO)
- M5 Phone call
 - Safety focused phone call after 5 months of investigational treatment
- M6 (end-of-intervention visit) visit is replaced by a telephone call
 - phone call for safety and fora reduced number of efficacy measurements (ePRO)
- M7.5 Phone call
 - Safety focused phone call after 7.5 months of investigational treatment
- M9 visit

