Safety of study patients and investigators should be the priority during COVID-19 outbreak. Only ePROs (SF36, SARQoL, TSD-OC and Pat-D will be assessed during this period until further guidance. An extension of the treatment period for a total period of 9 months of intervention will enable the full assessment of the safety and efficacy of the investigational product for a significant part of the population randomized in this study, while staying in compliance with good clinical practice (GCP), and minimizing risks to trial integrity during the COVID-19 pandemic.

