3 STUDY DESIGN

3.1 General study design

This study is a three arm (2 doses versus placebo), randomized, double-blind, placebo-controlled parallel design phase 2 clinical trial, with total study duration of 33-35 months.

This comparative clinical trial evaluates the effects of a 6-month treatment duration, based on the hypothesis that physical function of sarcopenic, older subjects with an initial degree of mobility disability (SPPB≤8) will be meaningfully improved after 6 months of oral treatment with BIO101 (in at least one of the two tested doses) with respect to placebo.

This multi-site study will enroll 231 community dwelling older adults (men or women \geq 65 years) reporting a loss of physical function over the previous 6-12 months and considered at risk of mobility disability to undergo screening tests for inclusion in the study. Included subjects will be randomized in a 1:1:1 ratio, for one of the 3 arms of treatment in a blinded manner.

Safety of study patients and investigators should be the priority during COVID-19 outbreak. Only ePROs (SF36, SARQoL, TSD-OC and Pat-D) will be assessed during this period until further guidance. An extension of the treatment period for a total period of 9 months of intervention will enable the full assessment of the safety and efficacy of the investigational product for a significant part of the population randomized in this study, while staying in compliance with good clinical practice (GCP), and minimizing risks to trial integrity during the COVID-19 pandemic.

Bias are minimized by the use of identical therapeutic units whose number is automatically assigned via an eCRF embedded algorithm after the Investigator confirms randomization of a subject. The Study Flow Chart is presented in **Figure 1**.

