8.7.6.1 Sensitivity Analyses of Missing data by Using Bayesian Multiple Imputation (MI) Methods

Bayesian MI method will be used to impute 400-m gait speed for the non-completers. The technical details of the Bayesian MI method have been described in publication¹⁰. Briefly, assumed that the 400-m gait speed data collected at 3, 6/ 9 months followed a multivariate normal distribution. The 400-m gait speed for the non-completers was imputed subject to the constraint that the value is less than 0.44 m/s. All imputations were performed separately for the two intervention groups. The SAS macro used to implement the procedure is detailed in Supplementary Appendix S1.

Two different Bayesian imputation models were used. The unadjusted Bayesian imputation model relied solely on the assumption that the 400-m gait speed of the non-completers was left-censored. . Non-completers include subjects who did not complete the test and discontinued from study, including discontinued due to COVID-19. The adjusted Bayesian imputation model used the baseline 400-m gait speed as a covariate in the imputation process.

Subsequently, we conducted analyses for the longitudinal 400-m gait speed data using both the simplistic imputation and the Bayesian MI methods. For the Bayesian MI method, analyses were performed on each of the 25 multiply imputed datasets obtained from the adjusted Bayesian imputation models. The results were then combined using Rubin's method carried out in SAS PROC MIANALYZE for valid statistical inference¹¹. In all analyses, linear mixed-effects models were fit with unstructured variance-covariance matrices. The models contained main effects for intervention assignment and visit and the intervention by visit interaction. Baseline 400-m gait speed was used as a covariate. Least square means were estimated for each intervention group at each follow-up visit. An example of the SAS program is included in Supplementary Appendix S2.

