Appendix S1 - A SAS macro for Implementing the Bayesian Multiple Imputation Method

Program: impute car only data.sas Purpose: Bayesian MI method for left-censored data Author: Macro Note: multivariate normal data is in wide format including id, varlist values that are < LOD and need imputed are replaced with LOD varlist: variables need imputation, whether MAR or CAR (coarsening at random) covlist: variables that have no missing data are considered as covariates indexlist: binary variables that identify whether the observations of the corresponding variable in the varlist needs imputed this is useful when some values in the varlist are <LOD but do not need to be imputed; otherwise it is just an indicator for data missing or not noimpute: the value that indexlist variables takes if the observations of the variables in the varlist do not need to be imputed lboundlist: impute values > lbound, . represent no bound LODlist: the limit of detection for the normal data, . represents no LOD iteration-# of iterations for Gibbs sampler to converge ndata-# of multiply imputed data sets for each chain nchain-# of independent Markov chain interval-# thinning parameter of the MCMC chain output ndata imputed data sets from each of the nchain chains: can use ndata data sets from nchain different chains or ndata data sets from a single chain (data set called midata org) varlist, indexlist, lboundlist, lodlist need to have the same dimension this program does not track parameter estimates due to memory constraints */ %macro coarsen(data,id,varlist, covarlist,indexlist, noimpute, lboundlist,lodlist,iteration,ndata,nchain,interval, initialseed); proc iml; * read in data; use &data; read all var {&varlist} into zorg; read all var {&id} into pid; %if &covarlist ne %then %do; read all var {&covarlist} into xcov; %end:

read all var {&indexlist} into indexorg; %end; close &data;

Statistical Analysis Plan Protocol Number: BIO101-CL03

%if &indexlist ne %then %do;

Version Final 2.0, Date: 04JUN2021

```
* sample size;
n=nrow(zorg);
call symput('totaln',left(char(n)));
* dimension of multivariate;
p=ncol(zorg);
call symput('dim',left(char(p)));
* dimension of covariates with no missing data;
%if &covarlist ne %then %do;
pcov=ncol(xcov);
%end;
%else %do;
pcov=0;
%end;
* identify LOD for each variable;
%let li=1;
%do %while (%scan(&lodlist, &li, ' ') ne );
%let lod&li= %scan(&lodlist, &li, ' ');
lodorg=lodorg || &&lod&li;
%let li = %eval(&li+1);
%end;

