%if (&t=%eval(&iteration-&interval * (&nmi-1)) ) %then %do;
impute=j(n,1,&chain)||j(n,1,mi)||pid||znew;
* rearrange to the original variable order;
impute org=j(nrow(impute),p+3,0);
do m=1 to p;
impute org[,m+3]=impute[,rvarorder[m]+3];
end;
impute org=impute[,1:3]||impute org[,4:p+3];
midata org=midata org//impute org;
mi=mi+1;
%let nmi=%eval(&nmi-1);
* save memory space;
store impute impute org;
free impute impute_org;
%end; /* this goes with the output loop */
```

Statistical Analysis Plan Protocol Number: BIO101-CL03 Version Final 2.0, Date: 04JUN2021

```
%end; /* this goes with the iteration loop */
%end; /* this goes with the nchain loop */
* get variable names for output dataset;
vlist="&varlist";
 %do vi=1 %to &dim;
vname&vi='mi_'+scan(vlist, &vi);
call symputx("varname&vi", vname&vi);
%end;
* note that all variables in the output dataset contained imputation of
missing and left-censored data;
create midata_org from midata_org
[colname={'chain' '_imputation_' "&id"
%do vi=1 %to &dim;
"&&varname&vi"
%end;
 }];
append from midata_org;
quit;
%mend;
* %coarsen(data=walk,
           id=pidn,
           varlist=speed m3 speed m69 speed lod m3 speed lod m69,
           indexlist=complete m3 complete m69 complete m3 complete m69
           noimpute=1,
           covarlist=speed m0,
           lboundlist=0 0 0 0,
           lodlist=. . 0.44 0.44,
           iteration=2000,
           ndata=5,
           nchain=5,
           interval=100.
            initialseed=155504946);
```

Statistical Analysis Plan Protocol Number: BIO101-CL03

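### The COVID-19 imputation of missing gait speed leaves out the PF-10 scores that were still collected while walks were suspended

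*Protocol*

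**What the plan says.** **Data collection.** Protocol 2.2 (COVID-19 pandemic) states: "Only ePROs (SF36, SARQoL, TSD-OC and Pat-D will be assessed during this period until further guidance". SAP 3.1 repeats it. The protocol synopsis adds: "In addition, study questionnaires will be administered and study drug intake will also continue to be monitored following the same schedule". In Protocol 1.3 the "M6 (end-of-intervention visit) visit is replaced by a telephone call", described as a "phone call for safety and fora reduced number of efficacy measurements (ePRO)"; the M3 visit is treated in the same way. The schedule table has SF-36 (which contains PF-10), SarQoL and TSD-OC at both M3 and M6, and PAT-D at M6 but not M3.

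**Imputation.** SAP 8.7.6.1 takes gait speed at M3 and M6/M9 as multivariate normal. The unadjusted model has no covariate. For the other: "The adjusted Bayesian imputation model used the baseline 400-m gait speed as a covariate in the imputation process". The 25 datasets that are analysed come from this adjusted model. Imputed speeds for non-completers are held below 0.44 m/s, and non-completers are said to include COVID-19 discontinuations. In the Appendix S1 call, the variables to be imputed are all gait speeds, two with no limit and two with a limit of 0.44, and the covariate entry is "covarlist=speed m0".

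**Primary model.** The MMRM in SAP 8.7.1.1 has treatment, visit, centre, gender, treatment by visit and baseline. It has no questionnaire term.

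**The concern.** The imputation was added because COVID-19 removed walks. In the same period the plan went on recording PF-10, which the protocol itself regards as an effective measure of mobility disability. If the loss of a final walk is related to current function, for example because participants who feel worse decline the extension to M9, then baseline speed and an M3 walk may not capture that relation. Where the M3 walk was cancelled too, the model has nothing after baseline to work from. PF-10 at M3 and M6 could carry the missing information.

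At stake is how far this sensitivity analysis can correct for the COVID-19 losses. The protocol (9.2) expects non-evaluable withdrawals above 20% but gives no figure.

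**Working it through.** **1. Which variables enter.**

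| Model | Predictors of gait speed | Questionnaires |
|---|---|---|
| Primary MMRM (8.7.1.1) | Treatment, visit, centre, gender, baseline speed, other walk | None |
| Unadjusted imputation (8.7.6.1) | Other walk | None |
| Adjusted imputation (8.7.6.1, Appendix S1) | Other walk, baseline speed | None |

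SAP 8.7.3.1 does consider multiple imputation for PF-10, but as an outcome with gaps, not as a predictor of gait speed.

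**2. Design figures.** For a difference of 0.10 m/s, SD 0.20, two-sided 5% and 80% power, n = 2 × (1.96 + 0.84)² × 0.20² / 0.10² ≈ 63 per group; the t-test version gives 63.8. The plan's 64 reproduces. The 231 randomised give 231 / 3 = 77 per arm.

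**3. Bias without the 0.44 limit.** Inputs from the plan: 77 per arm, SD 0.20, true difference 0.10 m/s. Assumed, because the documents do not say: 30% of M6/M9 walks missing; gait-speed change correlates r = 0.3 or 0.5 with PF-10 change and 0.5 with the M3 walk; in one arm the log-odds of a missing walk change by 1 per SD of PF-10, and in the other arm walks are missing at random. Missing changes are filled by regression within arm, on the M3 change alone or on the M3 change plus PF-10 change. Mean estimated differences over 4000 simulated trials:

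| Arm affected | r | Without PF-10 | With PF-10 |
|---|---|---|---|
| Placebo | 0.3 | 0.087 | 0.100 |
| Placebo | 0.5 | 0.080 | 0.101 |
| Active | 0.3 | 0.112 | 0.100 |
| Active | 0.5 | 0.120 | 0.099 |

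Repeated simulations gave 0.080 to 0.091 and 0.109 to 0.120 without PF-10, and 0.098 to 0.101 with it. The bias is therefore about 0.01 to 0.02 m/s in either direction. The standard error is 0.037 to 0.038 both ways. With the same mechanism in both arms, both methods give about 0.10.

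**4. Bias with the 0.44 limit.** The limit is the 15-minute criterion: 400 m / 900 s = 0.444 m/s. Same settings, 1500 runs, with an assumed baseline mean of 0.75 to 0.95 m/s and SD 0.20, and every missing walk drawn below the limit:

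| Arm affected | r | Without PF-10 | With PF-10 |
|---|---|---|---|
| Placebo | 0.3 | 0.063–0.064 | 0.065 |
| Placebo | 0.5 | 0.054–0.056 | 0.056–0.060 |
| Active | 0.3 | 0.082–0.084 | 0.081–0.082 |
| Active | 0.5 | 0.089 | 0.086–0.088 |

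PF-10 moves the estimate by at most about 0.004 m/s. The limit outweighs any predictor.

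**5. Precision.** Let r now be the partial correlation of PF-10 with the walk, given baseline and M3. Effective n per arm = 1 / [(1 − r²)/n_walk + r²/n_PRO]. With 30% missing, n_walk = 77 × 0.7 = 53.9. If every participant has a questionnaire, n_PRO = 77. For r = 0.4: 1 / (0.84/53.9 + 0.16/77) = 56.6. Over r = 0.2 to 0.6 the range is 54.6 to 60.4, and power goes from 73.8% to between 74.3% and 78.5%. If only half of those without a walk have a questionnaire, the gain is roughly half.

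**6. Feasibility.** The macro note reads: "varlist: variables need imputation, whether MAR or CAR" (the latter meaning coarsening at random). A full stop in the limit list means no limit, and the size of the regression step follows the number of variables supplied. PF-10 can be added without new code.

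**The case against.** The case against is substantial, and parts of it stand.

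- **The bias needs a difference between arms.** Protocol 2.3.4 cancelled on-site visits for all active participants, whatever their function or arm, in a double-blind trial. If both arms lose walks in the same way, PF-10 changes little. This stands. Differential loss is possible, but the documents give no evidence of it.
- **The 0.44 m/s limit.** As 8.7.6.1 is worded, COVID-19 discontinuers are imputed below the limit, and adding PF-10 then does almost nothing. This stands, and it is why the fix must also settle which participants are limited. A reader might infer that PF-10 alone would restore the full effect. Step 4 shows that it would not.
- **Other analyses exist.** A reader might infer that this is the only missing-data analysis of the primary endpoint. It is not. The SAP also plans an ANCOVA on the last assessment on treatment, a responder analysis counting missing as non-response (both 8.7.2), a simplistic imputation (8.7.6.1) and a before/after COVID-19 classification (8.7.6). The protocol has an Adjudication Committee that may use the medical dossier or a proxy such as the 4 m walk. None of these is described as using the questionnaires to predict gait speed, and 8.7.6.1 is the only multiple imputation of the endpoint.
- **Few participants may benefit.** An M9 walk replaces a missing M6 walk (SAP 8.7), and early leavers may have no M6 questionnaire. This stands: only participants with a remote questionnaire but no end-of-treatment walk gain.

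**Conclusion.** The omission is real: no questionnaire enters any model of gait speed, although PF-10 was scheduled remotely at M3 and M6 when walks could not be done. Adding it as an auxiliary variable is a worthwhile, low-cost improvement to a sensitivity analysis. Under the assumptions in step 3, and with no limit on the imputed speeds, it removes a bias of about 0.01 to 0.02 m/s on a 0.10 m/s effect. With the same mechanism in both arms, or with the 0.44 m/s limit applied to these participants, the change is at most about 0.004 m/s. The missing fraction, the correlations and the missingness mechanism are all assumed.

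The documents do not support the inference that the primary MMRM is invalid. An MMRM under missing at random without questionnaire data is a legitimate primary choice.

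**What to change.** Amend SAP 8.7.6.1 and the Appendix S1 call before unblinding; SAP 7.1.3 already foresees changes to the imputation by amendment.

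1. Separate walks missing because of COVID-19 cancellation or discontinuation from walks attempted and not completed. Keep the 0.44 m/s limit for the second group only.
2. Impute the first group through the no-limit speed variables already in the call, and state which imputed speed column feeds the analysis for each group.
3. Add PF-10 at M3 and M6 to varlist as auxiliary variables with no detection limit, and lengthen indexlist, lboundlist and lodlist to match. PAT-D could be added at M6 only.
4. Run the imputation separately in each of the three arms (8.7.6.1 speaks of two groups). Leave the analysis model for gait speed unchanged.
5. Report, by arm, how many participants have a remote PF-10 but no end-of-treatment walk, so that the reader can see how much the change could matter.

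The cost is a few SAP sentences and a longer macro call. The data are already collected. The downside is a slightly larger imputation model.

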2.3 RISK/BENEFIT ASSESSMENT

2.3.1 KNOWN POTENTIAL RISKS

Potential risks are related to the long-term administration of an investigational drug to participants suffering from multiple chronic diseases.

BIO101 was well tolerated in healthy elderly volunteers receiving up to 450 mg b.i.d. for 14 days. Based on non-clinical safety (26-week studies **example 1**, safety pharmacology and phase 1 results, both immediate and long-ranging risks can be considered as low.

The active ingredient in BIO101, 20E, may become a restricted substance, which is not allowed to be used in sport competitions. The reason is that there is a tendency to use it as an anabolic agent. Since BIO101 contains a high concentration of 20E at a dose that is much higher than the one that appears in nutritional supplements, there is concern that non-sarcopenic individuals may want to use BIO101 illicitly. Participants in this study will be warned and instructed to not allow anyone to gain access to their medication and to use only according to the medication instructions provided in the drug kits.

In addition,

putative mechanism of action through activation of the MAS receptor and potential impact on the renin–angiotensin–aldosterone system (RAS) requires attention. A special surveillance and precaution will be taken with events that could theoretically indicate presence of orthostatic hypotension (OTH), including dizziness and presyncope related to orthostatic changes and actual measurements. In addition, events that comply with the clinical definition of OTH (i.e. decrease in systolic blood pressure of 20 mm Hg or a decrease in diastolic blood pressure of 10 mm Hg within three minutes of standing when compared with blood pressure from the sitting or supine position) will require special attention even without symptoms.

There are limited risks linked to the execution of the functional tests, e.g. falling during a test. The investigational site staff will put in place adapted surveillance, adequate prevention including cancellation or postponing of a planned test, and adapted emergency care in order to prevent, limit and appropriately and timely treat possible adverse events.

All AEs will be reported as per standard pharmacovigilance procedures (Section 8.4).

